The aim is to investigate the effect of sevoflurane inhalational versus propofol intravenous anaesthesia on expression of hypoxia-inducible factor 1 (HIF-1), circulating tumour cells, DNA damage and biomarkers of immunity and inflammation in patients with hepatocellular carcinoma undergoing open hepatectomy.

Aim 1: To investigate the changes in gene expression and plasma concentrations of inflammatory biomarkers (HIF-1, IL-6, and TNF-alpha) induced by surgery and the effects of different methods of anaesthesia on this expression.

Aim 2: To investigate the changes in DNA damage induced by surgery and the effects of these two different methods of anaesthesia on this damage.

Aim 3: To investigate changes in circulating tumour cells pre, intra and post-surgery

Aim 4: To follow-up patients post tumour resection for three-year survival and investigate differences in survival between the TIVA and sevoflurane cohorts.

Aim 5: To investigate the difference in post-operative pain and post-operative morphine consumption in patients anaesthetized with propofol versus sevoflurane.

Background of Research

Cancer remains a leading cause of morbidity and mortality, despite continued advances in management and treatment strategies. In 2014, 'malignant neoplasms' was the leading cause of death for both sexes in Hong Kong, accounting for 30.2% of all registered deaths [1]. Of these, liver cancer, defined as malignant neoplasm of the liver and intrahepatic ducts, has been the third leading cause of cancer death in Hong Kong for many years. In 2014, 1,585 patients died from liver cancer, accounting for 11.5% of all cancer deaths [2]. In general, the age-standardized death rate due to liver cancer was higher in males than females, with a decreasing trend in age-standardized death rates in recent years [2]. With the ageing population and the rising incidence of cancer diagnoses, anaesthesiologists are frequently managing patients with cancer in their daily practice.

[figure not shown]

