
 - Contraindication to general anaesthesia - Autoimmune / Chronic inflammatory diseases e.g. Systemic Lupus Erythematosus (SLE), Rheumatoid Arthritis (RA) etc. - Chemotherapy in the past year - Steroid therapy - Surgery for tumour removal in the past year - patients post liver transplantation 	
 - Regional Anaesthesia 
Administration of:
 
 - Nitrous oxide - Inhalational agents (with the exception of sevoflurane)

Pre-operative care

Pre-operative assessment will be performed at the preadmission clinic or at the general ward. Patients will be fasted for intake of solid food for 6 hours and clear liquids for 2 hours. Sedative premedication will not be prescribed.

Anaesthesia and intraoperative care

SEVO Group

Patients from the SEVO group will be anaesthetized according to the following protocol:

On arrival at the operation theatre, an intravenous cannula will be inserted. Standard monitoring with pulse oximeter, non-invasive blood pressure, and three-lead electrocardiogram will be applied prior to induction. Non-invasive blood pressure (NIBP) will be checked at least every 5 minutes throughout the operation. An arterial line may be inserted at the discretion of the anaesthetist before or after induction, with invasive blood pressure monitoring in lieu of NIBP if deemed necessary. Additional intravenous cannulas or central lines may also be inserted to facilitate fluid therapy, measure the central venous pressure or administer drugs, also at the discretion of the attending anaesthetist.

Anaesthesia will be induced with titrated, manual propofol injection of 1-2 mg.kg⁻¹. Remifentanil infusion will be given for analgesia at a rate of 0.1 – 0.35 mcg.kg.min⁻¹ as required, according to haemodynamic parameters. Cisatracurium 0.15 mg.kg⁻¹ or atracurium 0.5 mg.kg⁻¹ will be used for muscle relaxation. Tracheal Intubation will be performed after induction of general anaesthesia. General anaesthesia monitoring will be used. Sevoflurane at 0.5- 1 MAC, air and oxygen will be used for maintenance of general anaesthesia. Processed EEG (BISTM) will be utilized to monitor depth of anaesthesia, aiming at a BIS value of 40-60. FiO₂ will be kept between 35-50% to maintain and SaO₂ of > 95%. Further muscle relaxants can be given during the operation if required.

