Patients will be followed up for three-year survival.

Blood-taking (*a total of 15mls on each occasion*) will take place at four time-points:

1. *Pre-operative*

This is for baseline assessment, and will be taken in the operation theatre from the IV cannula before induction of anaesthesia.

2. *Intra-operative*

This time point will be up to the discretion of the surgeon. As soon as the surgeon deems the tumour to be resected, the attending anaesthetist will take the blood sample.

3. *Immediately post-operative*

This will be taken outside the operating theatre 30 mins after arrival in the recovery room.

4. *24 hours post-surgery*

This will be taken in the general ward or intensive care unit (ICU).

Biochemical assessment of blood samples

Around 15mls of venous or arterial blood will be taken at each time point, and will be analysed for the following biomarkers:

Table 1

Biomarker	Sample	Method
Gene expression (HIF-1, IL-6, TNF-alpha)	RNA/cDNA	PCR
DNA damage (Comet Assay)	White cells	manual
hsCRP	Plasma	Commercial Kit
Glutathione Peroxidase	RBC	Commercial Kit
Superoxide dismutase	"	"
8-oxoGuo, 8-oxodG	Plasma	"
IL-6, TNF-alpha, HIF-1	plasma	ELISA
Circulating tumour cells	Whole blood	Isolation by Size of Tumour Cells

Primary outcome

The primary outcome of this study is the detection of a two-fold difference between the pre-operative blood sample and 24-hour post-operative blood sample in HIF-1 gene expression in the SEVO group, and a less than two-fold difference in the same samples of the TIVA group.

The secondary outcome is a reduction in the incidence of two-year recurrence from 40% in the SEVO group to 20% in the TIVA group.

Other secondary outcomes are listed in Table 1.

Sample size calculation

Using the primary outcome of HIF-1 gene expression of at least 2-fold difference between time points, power of 0.9 and standard deviation (SD) of 0.9, 22 patients are required in each group. To account for drop-outs, 25 patients will be recruited into each group, making a total of **50** patients.

Using the secondary outcome of two-year recurrence after hepatectomy of around 40% and an expected two-year occurrence of 20% in the TIVA group, 108 patients must be recruited into the study (total of 216 in both groups, to account for potential drop-outs **220** patients will be recruited) with an alpha of 0.05 and power of 0.9.

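### Sampling vessel is not held constant or recorded, so within-patient biomarker changes (Aim 3, Table 1, the primary HIF-1 contrast) can be mixed with a venous-to-arterial switch of unknown size and direction

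*Combined protocol and SAP*

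**What the plan says.** The combined protocol and SAP describes blood sampling in two adjoining places that do not agree.

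- The list of four blood-taking times, under Patient data collection, says that the pre-operative sample "will be taken in the operation theatre from the IV cannula before induction of anaesthesia". That makes baseline venous.
- The same list gives the other three samples a moment or a place but no vessel. For the intra-operative one: "As soon as the surgeon deems the tumour to be resected, the attending anaesthetist will take the blood sample". For the immediate post-operative one: "This will be taken outside the operating theatre 30 mins after arrival in the recovery room". The 24-hour sample is taken on the ward or in ICU.
- Biochemical assessment of blood samples then states: "Around 15mls of venous or arterial blood will be taken at each time point". Read literally, this covers baseline too.

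Access is left to judgement. Under Anaesthesia and intraoperative care: "An arterial line may be inserted at the discretion of the anaesthetist before or after induction", and "Additional intravenous cannulas or central lines may also be inserted to facilitate fluid therapy". A venous sample could therefore be peripheral or central.

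Aim 3 is "To investigate changes in circulating tumour cells pre, intra and post-surgery". The primary outcome compares HIF-1 gene expression in the pre-operative and 24-hour samples. Patient data collection does not list the vessel or site of each sample. Statistical analysis compares laboratory biomarkers between arms by chi-square and t tests, with no term for vessel.

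**The concern.** A change over time can be read as a biological change only if the measurement is made the same way each time. Here baseline is fixed as venous and the later samples are free, so any use of arterial blood falls on the later side of the contrast. If arterial and venous levels of a marker differ, the difference enters the time trend in one direction and does not average out. Randomisation does not help with a before-and-after contrast.

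Three kinds of result are exposed: the course of circulating tumour cells over surgery (Aim 3), changes in the other Table 1 biomarkers, and the pre-operative to 24-hour change in HIF-1 expression. The primary outcome is worded as a fold change within each arm, set against a two-fold mark. A vessel shift common to both arms would not cancel out of that criterion, although it would cancel out of a difference between arms.

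Because vessel is not a listed item, an analyst might have no means of finding or correcting a switch afterwards.

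**Working it through.** The plan gives no figure on this point, so there is none to reproduce. The check has two parts.

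**1. Does the text allow the vessel to change within a patient?**

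| Sample | Vessel stated in the time-point list | Allowed by the assay section |
|---|---|---|
| Pre-operative | IV cannula (venous) | venous or arterial |
| Intra-operative | none | venous or arterial |
| 30 minutes after reaching recovery | none | venous or arterial |
| 24 hours | none (ward or ICU) | venous or arterial |

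It does. Nothing requires one vessel across a patient's four samples, and nothing requires a switch.

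**2. What would a switch do?**

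Let R be the arterial-to-venous ratio of a marker, b = log2(R), and f the share of later samples that are arterial. Take baseline as all venous. Then, on the log2 scale:

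apparent mean change = true mean change + b × f

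so the apparent geometric-mean fold change equals the true one times R^f. The documents give neither R nor f. All values below are assumptions.

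| R | f = 0 | f = 0.5 | f = 0.8 | f = 1 |
|---|---|---|---|---|
| 0.5 | 1.00 | 0.71 | 0.57 | 0.50 |
| 1/1.5 | 1.00 | 0.82 | 0.72 | 0.67 |
| 1 | 1.00 | 1.00 | 1.00 | 1.00 |
| 1.5 | 1.00 | 1.22 | 1.38 | 1.50 |
| 2 | 1.00 | 1.41 | 1.74 | 2.00 |

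A two-fold change is 1 unit on the log2 scale. With R = 2 and f = 0.5 the shift is 1 × 0.5 = 0.5, half of that unit; with R = 1 it is zero. For tumour cells the table shows scale only, since a fold change needs positive counts and the Background describes patients (in colorectal cancer) with no detectable cells before surgery.

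**Between arms.** The bias on the log2 scale is b × (f_SEVO − f_TIVA). It is zero when the shares are equal. If the SEVO share were 20 points higher, the SEVO-to-TIVA ratio would be multiplied by 1.5^0.2 = 1.08 for R = 1.5 and 2^0.2 = 1.15 for R = 2; for the reciprocal values of R, by 0.92 and 0.87.

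**Noise with equal shares.** Read the SD of 0.9 in Sample size calculation as the SD of the log2 change with vessel held constant (an assumption; the scale is not stated), and take vessel choice as unrelated to the true change. Then

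SD = √(0.9² + b² × f × (1 − f))

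- b = 0.5, f = 0.5: √(0.81 + 0.0625) = 0.93. Required size grows by 0.8725/0.81 = 1.08.
- b = 1, f = 0.5: √(0.81 + 0.25) = 1.03. Required size grows by 1.06/0.81 = 1.31.

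**The case against.** The best reply is that the documents permit a switch without making it usual. The arterial line is optional, its frequency is not given, and ICU is named only as a place. A reader might infer a standard course of venous blood at baseline, arterial blood in theatre and recovery, and venous blood on the ward, and from it a spurious rise of 1.2- to 1.7-fold. The documents do not support either step. That range comes from assuming R of 1.5 to 2 and a switching share of 0.5 to 0.8; it leaves out R = 1, which gives no bias, and R below 1, which gives a spurious fall. Filtration of cells in the lungs and peripheral tissues is a plausible reason for a difference, but the documents report no arterial-venous difference. Optional central lines make the direction less certain still. This part of the reply stands.

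The randomised comparison is also largely protected. The only biomarker analysis specified is between arms, and the TIVA section says that monitoring and blood-pressure management follow the SEVO group. The attending anaesthetist knows the allocation and draws the intra-operative sample, so differential vessel use is possible, but nothing in the documents points to it.

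Raw changes over surgery are also affected by blood loss and fluid replacement, so a single vessel would not make them a clean measure of shedding. That is true, but vessel is the part that can be controlled or recorded cheaply.

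Finally, an analysis confined to same-vessel pairs could be costly. If 50% to 80% of patients switched, it would keep 25 to 10 of the 50 patients at the preliminary analysis, selected by a choice made after randomisation. This stands against using it as the main analysis.

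**Conclusion.** The gap is real and modest. The plan lets the sampling vessel vary with time within a patient and provides no listed record of it. Aim 3, changes in the other Table 1 biomarkers, and the pre-operative to 24-hour HIF-1 contrast can all carry a vessel effect.

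Its size and direction are unknown. It is nil if arterial and venous levels are equal or if all later samples are venous, and otherwise R^f, with both quantities assumed. The comparison of TIVA with SEVO is affected beyond added noise only if vessel use differs by arm. A reader might conclude that the between-arm results are biased; the documents give no evidence of that. The point is worth acting on because the remedy is cheap and the missing information may not be recoverable later.

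**What to change.** 1. Reconcile the time-point list with the assay section. Specify peripheral venous blood at all four time points where feasible, and at least for the pre-operative and 24-hour pair that carries the primary outcome.
2. Record vessel and site (peripheral venous, central venous or arterial) for every sample.
3. Keep all patients in the main analysis. Add a sensitivity analysis limited to same-vessel pairs, or adjusted for vessel, for Aim 3, the other Table 1 biomarkers and the HIF-1 contrast. Tabulate vessel by arm and time point.

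The cost is a sentence in the sampling section, one form entry per sample, and some extra venous draws where an arterial line would have been more convenient. The number of draws depends on how often arterial sampling would otherwise be used: at an assumed 50% to 80% it would involve 110 to 176 of the 220 patients (0.5 × 220 and 0.8 × 220), and far fewer if arterial sampling is rare. Blood volume and assays do not change. Recording the vessel is the essential minimum and should start before the planned preliminary analysis and publication at 50 patients.

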For this current study preliminary analysis and publication of data will be conducted after 50 patients have been recruited. Recruitment will continue until **220** patients have completed the study.

Statistical analysis

Patient demographics, disease stage, and surgery and laboratory biomarker data will be compared between TIVA and SEVO groups using chi-square and *t* tests as appropriate. The Kaplan–Meier method will be used to calculate the overall survival of patients from the date of surgery to the date of death; patients alive will be censored at the follow-up closure date. A Cox proportional hazard regression model will be used to compare the hazard of the two groups by using a univariate model.

Impact of the study and concluding remarks

Thousands of patients with a cancer diagnosis undergo surgery in Hong Kong every year. If it can be shown that anaesthetic technique can impact survival after tumour resection surgery, then this will inform both clinicians and patients regarding the most suitable method of anaesthesia for their particular situation. Through biochemical analysis of blood samples taken pre, intra, and post-surgery, the mechanisms through which anaesthetic techniques may mitigate cancer recurrence after hepatectomy can be elucidated.

References:

1. *Leading Causes of Cancer Deaths*. Healthy HK, Department of Health 2014 [cited 2016 October 12th]; Available from: http://www.healthyhk.gov.hk/phisweb/en/healthy_facts/disease_burden/major_causes_death/cancers/cancers/.
2. Zhu, R.X., et al., *Epidemiology of Hepatocellular Carcinoma in the Asia-Pacific Region*. Gut and Liver, 2016. **10**(3): p. 332-339.
3. Abrams, P. and J.W. Marsh, *Current approach to hepatocellular carcinoma*. Surg Clin North Am, 2010. **90**(4): p. 803-16.
4. Divatia, J.V. and R. Ambulkar, *Anesthesia and cancer recurrence: What is the evidence?* Journal of Anaesthesiology, Clinical Pharmacology, 2014. **30**(2): p. 147-150.
5. Heaney, Á. and D.J. Buggy, *Can anaesthetic and analgesic techniques affect cancer recurrence or metastasis?* British Journal of Anaesthesia, 2012. **109**(suppl 1): p. i17-i28.
6. Grove, C.S. and G.S. Vassiliou, *Acute myeloid leukaemia: a paradigm for the clonal evolution of cancer?* Disease Models & Mechanisms, 2014. **7**(8): p. 941-951.
7. Vinay, D.S., et al., *Immune evasion in cancer: Mechanistic basis and therapeutic strategies*. Seminars in Cancer Biology, 2015. **35, Supplement**: p. S185-S198.

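### The HIF-1 primary outcome is worded as two within-arm two-fold conditions, no between-arm test is tied to it, and its sample size is incompletely documented

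*Combined protocol and SAP*

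**What the plan says.** - **Aims and Objectives, Aim 1**: the interest is in changes in expression "induced by surgery and the effects of different methods of anaesthesia on this expression". The second half of that aim compares the arms.
- **Primary outcome**: "the detection of a two-fold difference between the pre-operative blood sample and 24-hour post-operative blood sample", continuing "in HIF-1 gene expression in the SEVO group, and a less than two-fold difference in the same samples of the TIVA group". The variable (HIF-1 gene expression), the two samples and a fold metric are fixed. The direction of the difference is not stated, nor whether two-fold refers to each patient or to the arm mean.
- **Sample size calculation, HIF-1**: "HIF-1 gene expression of at least 2-fold difference between time points, power of 0.9 and standard deviation (SD) of 0.9", giving 22 per group, raised to 25 for drop-outs (50 in total). The difference is between time points, not between arms. No alpha, scale or TIVA value is given, and the SD is not identified as that of a change or of a single sample.
- **Sample size calculation, recurrence**: this is the only place where an alpha appears, "with an alpha of 0.05 and power of 0.9".
- **Sample size calculation, closing paragraph**: "preliminary analysis and publication of data will be conducted after 50 patients have been recruited", with recruitment continuing to 220.
- **Statistical analysis**: "laboratory biomarker data will be compared between TIVA and SEVO groups using chi-square and" t tests, whichever suits. The section does not mention the primary outcome.

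**The concern.** A randomised comparison is decided by the contrast between arms. Two separate statements, one per arm, about which side of a threshold a result falls do not form that contrast: two arms can straddle two-fold and be almost identical, or lie on the same side and differ clearly. The plan contains the ingredients of a proper comparison but does not say which one decides the primary outcome. A t test on change, a t test on the 24-hour value, a chi-square on the proportion of patients reaching two-fold, and a reading of the arm means against two-fold are all compatible with the text. They can give different primary results and they have different power. Nothing fixes the choice before the data are seen, and because results are to be published after 50 patients, the ambiguity reaches the first report.

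**Working it through.** **Inputs from the protocol.** SD 0.9, power 0.9, two-fold, 22 (25) per group. **Assumed, because the protocol is silent:** two-sided alpha 0.05; change analysed on log2 (two-fold = 1.0), with ln as the alternative (two-fold = 0.693); SD 0.9 is that of the change unless stated otherwise.

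**1. Can 22 be reproduced?** Normal formula: n per arm = 2(1.960 + 1.282)² × 0.9² / d² = 17.02 / d².
- d = 1.0 (log2): 17.02, so 18; 19 by exact t.
- d = 0.693 (ln): 35.4, so 36; 37 by exact t.
- d = 0.9 (difference equal to the SD): 21.01, so 22; exact t power at 22 is 0.8997.
- d = 1.0 with two-sided alpha 0.025: power at 22 is 0.909.

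So 22 can be reached, but each of these routes to it needs a choice that the protocol does not state.

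**2. Arm-mean reading (illustration).** SE of the difference = 0.9 × √(2/22) = 0.271; df 42; 95% half-width 0.548.

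| Observed SEVO v TIVA | Wording met? | log2 difference | t | p | Ratio (95% CI) |
|---|---|---|---|---|---|
| 2.1 v 1.9 | yes | 0.144 | 0.53 | 0.60 | 1.11 (0.76 to 1.62) |
| 1.7 v 1.0 | no | 0.766 | 2.82 | 0.007 | 1.70 (1.16 to 2.48) |

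On ln the two p-values are 0.71 and 0.057.

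With no anaesthetic effect, the chance that the wording is met is P(SEVO mean ≥ two-fold) × P(TIVA mean < two-fold). The SE of one mean is 0.9/√22 = 0.192.
- Both arms truly two-fold: 0.5 × 0.5 = 25%, the maximum.
- Both truly 1.5-fold: the threshold is (1 − 0.585)/0.192 = 2.16 SE away, giving 1.5% (6% on ln).
- Neither arm changes: near 0.

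**3. Per-patient reading, chi-square on responders.** P(log2 change ≥ 1) is 0.50 for SEVO at two-fold and 0.133 for TIVA unchanged. Exact power of the uncorrected chi-square, TIVA unchanged:

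| True SEVO fold | 22 per arm | 25 per arm |
|---|---|---|
| 2.0 | 77% | 84% |
| 2.2 | 87% | 92% |
| 2.5 | 96% | not needed here |

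**4. Between-arm t test on log fold change, SEVO two-fold, 22 per arm (noncentral t).**
- SD 0.9 on log2: 95% with TIVA unchanged, 87% at 1.10-fold, 69% at 1.25-fold, 32% at 1.5-fold.
- SD 0.9 on ln, TIVA unchanged: 70%.
- SD 0.9 of a single sample on log2, TIVA unchanged: SD of change = 0.9 × √(2(1 − ρ)) = 1.27, 1.06, 0.90, 0.70 for ρ = 0, 0.3, 0.5, 0.7; power 72%, 86%, 95%, over 99%.
- On log2, 90% power corresponds to a ratio of 1.87 at 22 per arm, so TIVA may rise to 2/1.87 = 1.07-fold. At 25 per arm the ratio is 1.79 and the limit about 1.12-fold.

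**The case against.** The strongest reply is that the primary-outcome sentence states an expected pattern, not a success rule. The next sentence does the same for recurrence (40% falling to 20%), and nobody would read that as a decision rule. The only tests planned for biomarkers are between-arm tests; no within-arm test appears. This stands. A reader might infer that the trial will be declared positive when the SEVO mean reaches two-fold and the TIVA mean does not, or that HIF-1 has no between-arm test at all. The documents support neither inference: the arm-mean reading is one of several, and a generic between-arm comparison of biomarkers is planned. The gap is that this comparison is not connected to the primary outcome.

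A second reply is that fixing SEVO at exactly two-fold is unfavourable, since the sample-size text allows at least two-fold. This also stands. At 2.5-fold with TIVA unchanged, the arm-mean wording is met 95% of the time and the responder chi-square has 96% power (log2, 22 per arm). It would therefore be wrong to say that a per-patient analysis necessarily falls short of 0.9.

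A third is that power, SD, the two-fold target and a drop-out allowance are all given. They are, so the calculation is incomplete, not absent, and the working does not show 22 to be an error.

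These replies do not supply the variable, scale, test and alpha for the primary outcome, and the between-arm contrast on which 22 rests remains unstated.

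**Conclusion.** The point holds in limited form. The primary outcome is worded as two within-arm conditions for a between-arm aim, and no test, variable or scale is assigned to decide it. Under one permitted reading (arm means), the wording can be met with no evidence of a difference and missed with clear evidence of one. The 25% chance of meeting it with no anaesthetic effect is a ceiling, reached only when both arms are truly two-fold. The HIF-1 sample size lacks alpha, scale, TIVA value, between-arm difference and the meaning of the SD; 22 is neither confirmed nor refuted. With SEVO two-fold and TIVA unchanged, t-test power at 22 per arm ranges from 70% to over 99% depending only on how SD 0.9 is read. All power and p-value figures rest on the assumed two-sided 0.05 and normally distributed log changes. Because this is the primary outcome and a first publication is planned at 50 patients, it should be settled before any HIF-1 data are compared by arm.

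**What to change.** - **Primary outcome.** Define it as the between-arm difference in log2(24-hour / pre-operative HIF-1 gene expression). Test it with one named two-sample t test at a stated two-sided alpha, and report it as a ratio of fold changes with 95% CI. Keep the within-arm two-fold results as description. A fully defined responder chi-square would also remove the ambiguity, but with SEVO at two-fold and TIVA unchanged it has 77% power at 22 per arm against 95% for the t test.
- **Sample size.** Restate it on that contrast with scale, alpha, SD of the change and assumed TIVA value, and quote the resulting power. The sponsor needs to confirm what SD 0.9 refers to.
- **Timing.** State before data are seen whether the 50-patient analysis or the final analysis is the HIF-1 primary test. The 50-patient analysis, for which 25 per arm was sized, is one option. If the final analysis is chosen, say how the early look is handled.

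**Cost.** The changes are to wording in three paragraphs; the samples and assays are already planned. The downside is that the quoted power becomes conditional on a stated TIVA value and SD scale, and may be below 0.9. If 0.9 proves to be on the ln scale, for example, 90% power would need 37 per arm, and the sponsor would have to accept lower power at 50 patients or place the primary test later.

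### 220 is both the number recruited with drop-outs included and the number who must complete, and two-year recurrence, its only basis, has no stated analysis

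*Combined protocol and SAP*

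**What the plan says.** The Primary outcome section sets as a secondary outcome a "reduction in the incidence of two-year recurrence from 40% in the SEVO group to 20% in the TIVA group". The Sample size calculation section turns this into "108 patients must be recruited into the study (total of 216 in both groups, to account for potential drop-outs", followed by 220 as the number to recruit. In that sentence 220 already contains the drop-outs.

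The section's last paragraph plans a preliminary analysis after 50 patients and then keeps recruitment open until 220 "patients have completed the study". In that sentence 220 excludes drop-outs. What counts as completing is not said.

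HIF-1, the primary outcome, needs far fewer patients: 22 per group, then "To account for drop-outs, 25 patients will be recruited into each group". Two-year recurrence is therefore the only stated reason for going from 50 to 220.

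The Statistical analysis section has two parts. The first reads "Patient demographics, disease stage, and surgery and laboratory biomarker data will be compared between TIVA and SEVO groups using chi-square" and t tests; recurrence is not in that list. In the second, the Kaplan-Meier "method will be used to calculate the overall survival of patients from the date of surgery to the date of death", and "patients alive will be censored at the follow-up closure date". A univariate Cox model follows, with no endpoint of its own named.

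**The concern.** The trial team cannot follow both enrolment sentences once a single patient is lost. One stops at 220 randomised, the other at some larger and unstated number.

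The outcome that fixes the trial's size also has no analysis. The sample-size formula implies a comparison of two proportions, but the analysis section does not provide one for recurrence. Its only censoring rule covers patients alive at follow-up closure, with death as the event. Someone who leaves follow-up at 14 months without recurrence, or dies at 14 months without recurrence, could be excluded, counted as recurrence-free, or censored. These choices give different power and different estimates. What is at stake is how many patients are enrolled, and whether the stated power of 0.9 applies to the recurrence comparison.

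**Working it through.** **Inputs.** From the Primary outcome and Sample size calculation sections: recurrence 0.40 v 0.20, alpha 0.05, power 0.9, 108 per group, 216 in total, 220 recruited. Sidedness is not stated; two-sided is assumed because it reproduces 108 (one-sided gives 89). No loss rate is stated, so 5%, 12% and 20% are assumptions. The 12% is only the inflation in the HIF-1 calculation, (25 − 22)/25; it is not a documented rate.

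**1. Reproduce 108.** With pooled proportion 0.30:

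n = [z₀.₉₇₅√(2 × 0.30 × 0.70) + z₀.₉₀√(0.40 × 0.60 + 0.20 × 0.80)]² / 0.20²

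= [1.960 × √0.42 + 1.2816 × √0.40]² / 0.04 = (1.2702 + 0.8105)² / 0.04 = 108.24 per group.

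The arcsine formula gives 108. The plan's figure stands.

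**2. Margin.** 220 − 216 = 4 patients, and 4/220 = 1.8%, for an outcome read at two years. The same section allows 12% for an outcome read at 24 hours.

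**3. The two enrolment rules, complete-case proportions.** If 220 are randomised, n = 110(1 − d) per group are evaluable at loss d, and power = Φ[(0.20√n − 1.2702)/0.6325]. If 220 must complete two years, the number to randomise is 220/(1 − d).

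| Assumed loss | Evaluable per group of 110 | Power, 220 randomised | To randomise for 220 completers |
|---|---|---|---|
| 0% | 110 | 90.5% | 220 |
| 5% | 104.5 | 89.0% | 232 |
| 12% | 96.8 | 86.5% | 250 |
| 20% | 88 | 83.1% | 275 |

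The two rules meet only in the first row.

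**4. Time to recurrence, losses censored.** Simulation: 200,000 runs, exponential recurrence and loss, no deaths without recurrence.

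| Assumed loss | Randomised | Log-rank | Difference in two-year Kaplan-Meier incidence |
|---|---|---|---|
| 5% | 220 | 90.3% | 90.3% |
| 12% | 220 | 89.2% | 89.0% |
| 20% | 220 | 87.8% | 87.3% |
| 12% | 228 | 90.2% | 90.1% |
| 20% | 240 | 90.4% | 90.0% |

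These totals leave little margin, and the Kaplan-Meier difference rejected a true null in 5.3% of runs at 12% loss, so they are approximate.

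The analysis also affects the estimate. Counting recurrences seen before loss, while excluding patients lost without one, gave mean incidences of 41.7% v 21.1% at 12% loss, against a true 40% v 20%.

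**5. Deaths without recurrence.** The documents give no rate; 5% and 10% by two years are assumed (20,000 runs each). The effect depends on what 40% and 20% mean.

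- If they describe recurrence hazards that deaths leave unchanged, deaths remove some recurrences. Power is then 0.895 and 0.886 (220 randomised, 5% loss), 0.890 and 0.879 (228, 12%), and 0.894 and 0.880 (240, 20%).
- If they are cumulative incidences with deaths already allowed for, power is 0.900 to 0.904 throughout.

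**The case against.** The strongest reply concerns the meaning of completing. If it means only giving the four blood samples up to 24 hours, the two totals differ only by early losses, and 232 to 275 is far too high. That reading is plausible: taken as two-year completion, the sentence works poorly as a recruitment rule, because completion would be known only two years after each entry. But the documents do not adopt it. It would also leave two-year losses with almost no allowance, since the margin remains 4 patients.

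A second reply is that the effect is small. This stands. With 220 randomised and losses censored, power is about 90%, 89% and 87 to 88% at the three assumed loss rates, before any effect of deaths. A reader might infer from the 83.1% that the trial is seriously underpowered. The documents do not support that: the figure needs both an assumed 20% loss and a complete-case test that the plan never specifies.

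A third is that the Cox sentence could be taken to include recurrence. It follows directly on overall survival and names no other event, so this has to be written down rather than presumed.

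Two further inferences should be resisted. One is that 108 per group is wrong; it is not. The other is that deaths without recurrence must lower power. On the reading closest to the plan's own term, incidence, they do not.

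**Conclusion.** The concern holds as an internal contradiction and an omission, with a modest numerical effect. The enrolment total is undetermined, and the outcome that sets it has no stated analysis and no rule for loss or for death without recurrence.

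If 220 is the number randomised and proportions are compared in complete cases, power is 89.0%, 86.5% or 83.1% at 5%, 12% or 20% loss, rather than 90%. If 220 is the number with two-year status known, power is kept but enrolment rises to about 232, 250 or 275. All of this rests on assumed loss rates and a two-sided uncorrected test. The outcome is secondary, and HIF-1 needs only 50 patients and is untouched. This should be corrected, but it does not threaten the primary result.

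Two side notes. If a Yates-corrected or Fisher test were intended, 220 completers would give 87.9%, and about 117 evaluable per group would be needed; the plan names neither test. The three-year survival horizon in Aims and Objectives and Patient data collection differs from the five-year mortality in the Introduction, but neither is the two-year outcome used for sizing.

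**What to change.** 1. **One enrolment rule.** State a fixed number to randomise in both sentences of the Sample size calculation section. Define completion (for example, two-year recurrence status known), and give the assumed loss rate with its matching power. The option with no extra patients is to keep 220 randomised and restate power: at 12% loss, about 86.5% for complete-case proportions, or about 89% for time to recurrence under the condition on deaths below.

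2. **A recurrence analysis.** Extend the Kaplan-Meier/Cox paragraph to time from surgery to recurrence, up to two years, in all randomised patients by assigned group. Censor losses at last contact, treat death without recurrence as a competing event, and report the difference in two-year cumulative incidence with its 95% CI. Other analyses would be defensible; the need is to name one before recurrence is compared by group.

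With this analysis, roughly 220, 228 or 240 randomised gives about 0.90 at 5%, 12% or 20% loss. The condition is that there are no deaths without recurrence, or that 40% and 20% are stated to be cumulative incidences. Otherwise, with recurrence hazards unchanged and 5% to 10% deaths assumed, the text should quote about 0.88 to 0.90.

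**Cost.** Wording in two sections, recording the recurrence date, modest analysis work, and either a slightly lower stated power or 0, 8 or 20 patients beyond 220 at the three loss rates.
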